#### 1. VERSION HISTORY

**Table 1. Summary of Changes** 

Version/ Date	Associated Protocol Amendment	Rationale	Specific Changes
1 14 Feb 2023	Amendment 1 23 Dec 2022	N/A	N/A

#### 2. INTRODUCTION

Sisunatovir (PF-07923568) is an orally administered RSV F-protein inhibitor being developed to target viral-host cell fusion for the treatment of adult and pediatric patients with RSV. This study is designed to assess safety and tolerability, pharmacokinetics, and food effect of multiple oral doses of sisunatovir. Additionally, the study is also designed to generate preliminary palatability data that will inform further development of formulations appropriate for pediatric Phase 2 and 3 studies.

This SAP provides the detailed methodology for summary and statistical analyses of the data collected in Study C5241006.

## 2.1. Modifications to the Analysis Plan Described in the Protocol

None.

## 2.2. Study Objectives, Endpoints, and Estimands

The following are the objectives and endpoints in this study. Estimand framework will not be applied to this Phase 1 study in healthy participants.

Objectives	Endpoints
Primary:	Primary:
• To characterize the safety and tolerability of multiple oral doses of sisunatovir in healthy adult participants	Assessment of TEAEs, clinical laboratory abnormalities, vital signs, and 12-lead ECGs
Secondary:	Secondary:
To characterize the PK of multiple oral doses of sisunatovir	• PK Parameters AUC tau , C max , T max , AUC tau (dn), C max (dn) for Day 1 and AUC tau , C max , T max , AUC tau (dn), C max (dn), CL/F R ac , R ac,Cmax ; and t 1/2 and V z /F (if data permits) post last dose on Day 5
• To evaluate the effect of food on the PK of multiple oral doses of sisunatovir	• The ratio of AUC tau and C max , on Day 5; T max on Day 5
To characterize the impact of liquid vehicles on the palatability of sisunatovir	Palatability Assessment Questionnaire Scoring Metrics: mouth feel, bitterness, sweetness, sourness, saltiness, tongue/mouth burn, overall liking
CCI	

#### 2.3. Study Design

This is a Phase 1 study that will be conducted in up to two cohorts.

Cohort 1 is a randomized, 2-part, crossover design. Part 1 has 3 periods, Periods 1 and 2 are double blind, sponsor open, placebo controlled crossover design to evaluate the safety and tolerability and PK of the planned 400 mg and 200 mg of sisunatovir given Q12 hours x 4 days plus 1 dose as 50 mg capsules in a fed state. Period 3, is an open label period to evaluate the food effect of the planned 400 mg of sisunatovir given Q12 hours x 4 days plus 1 dose in a fasted state. Part 2, Periods 4 7, is open label to assess the palatability of 50 mg of sisunatovir in 4 different vehicles (water, infant formula, apple juice, and saline) in a randomized crossover design.

Cohort 1 will include approximately 12 participants that will be randomized into 4 sequences with 3 participants in each sequence. Each sequence will receive treatment in a pre-specified manner (see Figure 1).

Over the first 2 periods, all participants are planned to receive (A) 400 mg and either (B) 200 mg plus matching placebo or (C) placebo dosed Q12 hours for 4 days plus 1 dose in the fed state. All participants in Period 3 will receive (D) 400 mg dosed Q12 hours for 4 days

plus 1 dose in the fasted state. A minimum 7-day washout period will occur between the last dose of Periods 1 and 2 and the first dose of Periods 2 and 3.

Prior to proceeding to Period 2 of Cohort 1, the Period 1 Day 5 PK up to 12 hours post-dose will be assessed. If the mean exposures (AUC or Cmax) at 400 mg in Period 1 exceeds the rat (most sensitive species) NOAEL, the doses for the subsequent period(s) will be capped to a dose that is not expected to exceed the rat NOAEL. Similarly, prior to proceeding to Period 3 of Cohort 1, the Periods 1 and 2 Day 5 PK up to 12 hours post-dose will be assessed, and if the mean exposures (AUC or Cmax) at 400 mg exceeds the rat (most sensitive species) NOAEL, the doses for the subsequent period(s) will be capped to a dose that is not expected to exceed the rat NOAEL. Furthermore, safety will also be assessed following each period and doses for subsequent periods may be reduced if the safety and tolerability of the previous dose was not deemed sufficiently tolerated.

During Periods 4-7 participants will taste sisunatovir 50 mg capsule content in different dosing vehicles ((E) water, (F) infant formula, (G) apple juice, and (H) saline) in a cross over manner and then spit out the drug with the intention of assessing the palatability of sisunatovir in different dosing vehicles. The palatability questionnaire will be completed for each vehicle, the questionnaire asks participants to assess each vehicle at 4 different time increments after tasting. At least 60 minutes will pass between tasting each vehicle. Period 4 may start after the last PK draw of Period 3.

Cohort 2 is an optional randomized, crossover cohort with 3 periods. Periods 1-2 are double blind, sponsor open, placebo controlled crossover design evaluating the safety, tolerability, and PK of sisunatovir administered Q12 hours for 4 days plus 1 dose in a fed state. Period 3, is an open label period to evaluate the food effect of sisunatovir given Q12 hours x 4 days plus 1 dose in a fasted state. Doses will not exceed 400 mg Q12 hours x 4 days plus 1 dose. Note that if the mean Day 5 exposure exceeds the rat NOAEL in Cohort 1, the dose in Cohort 2 will be capped at a dose that is not anticipated to exceed the rat NOAEL. Cohort 2 will be conducted at the discretion of the Sponsor after review of Cohort 1 data (including PK for at least periods 1 and 2), and there will be 2 sequences of 6 participants for Cohort 2.

[figure not shown]

Figure 1. Study Schema

# 3. ENDPOINTS AND BASELINE VARIABLES: DEFINITIONS AND CONVENTIONS

#### 3.1. Primary Endpoints

As listed in Section 2.2, the primary endpoint is related to safety/tolerability of multiple oral doses of sisunatovir and is described in Section 3.5.

#### 3.2. Secondary Endpoints

#### 3.2.1. PK parameters of sisunatovir

Blood samples for the PK analysis of susinatovir will be collected according to the Schedule of Activity given in the protocol.

Plasma PK parameters of sisunatovir will be derived (if data permit) from the concentration-time data using standard noncompartmental methods of analysis as outlined in Table 2. Actual PK sampling times will be used in the derivation of sisunatovir PK parameters when available. In the case that actual PK sampling times are not available, nominal PK sampling time will be used in the derivation of PK parameters.

Table 2. Plasma Sisunatovir PK Parameters Definitions

Parameter	Definition	Method of Determination
AUCıau	Area under the concentration- time profile from time zero to time tau (the dosing interval), where tau = 12 hours for BID dosing.	Linear/Log trapezoidal method.
$AUC_{tau}(dn)$	Dose normalized AUCtau	AUC tau /Dose
C max	Maximum observed plasma concentration	Observed directly from data
$C_{max}(dn)$	Dose normalized maximum plasma concentration	C max /Dose
T max	Time to reach C max	Observed directly from data as time of first occurrence
t ½	Terminal elimination half-life	$Log_e(2)/k_{el}$ , where $k_{el}$ is the terminal phase rate constant calculated by a linear regression of the loglinear concentration-time curve. Only those data points judged to describe the terminal loglinear decline will be used in the regression.
CL/F	Apparent clearance	Dose/AUC tau
$V_z/F^*$	Apparent volume of distribution	Dose/(AUCtau • kel)
Rac	Observed accumulation ratio for AUC	AUC tau Day5/AUC tau Day1
Rac,Cmax	Observed accumulation ratio for C max	$C_{max}$ Day5/ $C_{max}$ Day1

\* If data permit.

#### 3.2.2. Food effect on the PK of sisunatovir

The test/reference ratios for  $AUC_{tau}$  and  $C_{max}$  will be derived, with Treatment A (sisunatovir the highest tolerated dose Q12 hours administered under fed condition) as the test treatment and Treatment D (sisunatovir the highest tolerated dose Q12 hours administered under fasted condition) as the reference treatment. In addition, an estimate of the difference in  $T_{max}$  between Treatments A and D will be obtained from a non-parametric method (Hodges-Lehmann estimator).

## 3.2.3. Palatability of sisunatovir

The data collected for palatability assessment using the sponsor-provided palatability questionnaire will be numerically derived by measuring length (using a scale with gradations of at least 0.1 cm) of the "x" marked by the participant relative to the "good trait". For palatability assessment, the data used in the analysis will be transcribed and rescaled to a score from 0 to 100 from the raw measurements on the questionnaire.

#### 3.4. Baseline Variables

Baseline characteristics will be collected according to the schedule of activities (SoA) as specified in the protocol.

#### 3.5. Safety Endpoints

The following data will be considered in standard safety summaries (see protocol for collection days, baseline assessment, and list of parameters):

- Adverse events (AE)
- Laboratory data
- Vital signs data
- ECG results

#### 3.5.1. Adverse Events

Any adverse events occurring following start of treatment will be considered as treatment emergent adverse event (TEAE). If an AE starts on the same day as the first dose date, it will be considered treatment emergent unless the CRF data indicates otherwise via explicitly recording time for AE onset which was occurred before the first treatment dosing. Events that occur during follow-up within the lag time of up to 28-35 days after the last dose of study intervention will be counted as treatment emergent and attributed to the last treatment taken. Events that occur during the washout period between study periods will be counted as

treatment emergent and attributed to the previous treatment taken. The time period for collecting AEs ("active collection period") for each participant begins from the time the participant provides informed consent. The algorithm will not consider any events that started prior to the first dose date.

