Contraception check	X	X						X		X	X	Contraception check will occur with discharge activities at the end of Period 7.
FSH (post-menopausal women only)	X											
Urine drug testing	X	X										
12-Lead ECG (triplicate)	X		X				X	X	X		X	
 Single ECG for Screening. Pre-dose ECGs are triplicate of triplicates at 30 min, 20 min, and 10 min before the pre-dose meal in Periods I and 2, and 30 min, 20 min, and 10 min pre-dose in Period 3. All other ECGs are triplicate. DI and D5 schedule in Table 2.
Blood pressure and pulse rate	X		X				X	X			X	DI and D5 schedule in Table 2 .
HIV, HBsAg, HBsAb, HBcAbHCVAb	X											
COVID-19 related procedures	X	X	→	→	→	→	→	→	X	X	X	
 Performed per local procedures.

Table 1. Study Schedule of Assessment

Visit Identifier: Abbreviations used in this table may be found in Appendix 11 .	Sci'een	Periods 1-3							Periods 4-7	F/U 28-35 days aftel' last dose	ET	Notes
Days Relative to Day 1 for each period	Day- 28 to Day-2	Day-1	Day1	Day2	Day3	Day4	Day5	Day6	Day7	Day1		
Hom's Aftel' Dose			0	24	48							
Study intervention administration			X	X	X	X	X			X		
 For Periods 1-3: QL2 hours on Days 1-4; on Day 5 only the morning dose of study drug will be administered. The washout between last dose in previous period is 7 days (Periods 2 and 3 only). Periods 1 and 2 are dosed in the fed state and Period 3 is dosed in the fasted state.
Palatability Assessments										X		
 Palatability assessments will be completed at 1 min (immediately following dose), 5 min, 10 min, and 20 min after tasting dose in vehicle. There is an at least 60 minute washout between tasting each dose in vehicle.
Pharmacokinetic blood sampling			X	X	X	X	X	X			X	D2, D3, and D4 PK samples to be drawn before AM dosing. DI and D5 PK schedule in Table 2 .
Retained Research Sample for Genetics (Prep DI)			X									Prep DI Retained Research Samples for Genetics: If not collected on the designated collection day, collect at the next available time point when biospecimens are being collected in conjunction with a participant visit. To be collected during Period 1 only.

Table 1. Study Schedule of Assessment

Visit Identifier: Abbreviations used in this table may be found in Appendix 11 .	Screen	Periods 1-3							Periods 4-7	F/U 28-35 days afte'l' last dose	ET	Notes	

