Days Relative to Day 1 for each period	Day - 28 to Day-2	Day -1	Day 1	Day 2	Day 3	Day 4	Day 5	Day 6	Day 7	Day 1			
Hom's Aftel' Dose			0	24	48								
 Screening 28 days before the first dose. Follow-up may occur via telephone contact and 28 to 35 days after final dose. Periods 4-7 apply only to Cohort I. Periods 4-7 of Cohort I will occur on Day 7 of Period 3.
CCI													
CCI													
CRU discharge										X	X		
 Participants will discharge from the unit on Day 7 of Periods I and 2. After the last PK draw for Period 3 participants will immediately start Period 4. Participants will discharge from Period 7 after completing the final palatability assessment. See Section 8.4.3 for follow-up AE and SAE assessments.
Serious and nonserious AE monitoring	X	→	→	→	→	→	→	→	→	X	X		

Table 2. Periods 1-3 PK Days

Visit Identifier	For Periods 1-3 only															Notes
Study Day	Day 1 and Day 5											6		7		
Hours After Morning Dose	0	1	2	3	4	5	6	8	12	16	24	36	48			
Study intervention administration	X								X						
 • H12 dose should be given 12 hours \pm1 hour after H0 dose. • On D5 only the H0 dose will be given. 	
PK blood sampling	X	X	X	X	X	X	X	X	X	X	X	X	X		
 • H12 PK draw on D1 should be completed prior to evening dosing. • H16 sample day 5 only. 	
CCI																
Triplicate ECGs	X	X	X	X	X	X	X	X	X		X	X	X		
 • Pre-dose ECGs are triplicate of triplicates at 30 min, 20 min, and 10 min before the pre-dose meal in Periods 1 and 2, and 30 min, 20 min, and 10 min pre-dose in Period 3. • All other ECGs are triplicate. 	
Vitals	X				X			X			X					

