In Cohort 1 only, the palatability of sisunatovir will be assessed to aid in development of pediatric formulations. These assessments will be conducted at least 48 hours after the last dose in Period 3, to allow for collection of the final PK sample and complete assessment of and AEs associated with the multiple dosing scheme. Palatability will be assessed by all participants in 4 different vehicles with a minimum of 1 hour between each vehicle, 1 hour washout has been used for the palatability assessment of other compounds. In each case, the drug in vehicle will be swirled in the mouth and spat out since it is not necessary to consume the drug to assess palatability. API blend in Pharmacopeial grade water will be used to assess the taste of the API blend. API blend in formula milk and apple juice will inform whether food vehicles are likely to improve palatability. API blend in saline will enable understanding of whether saline reduces bitter perception and improves palatability.

The highest dose planned in this study (400 mg Q12 hours x 4 days plus 1 dose) is slightly higher than the previous highest multiple oral dose tested (350 mg Q12 hours x 5 days). For

this reason, in addition to AE monitoring, labs, vitals and ECGs will also be assessed. In order to facilitate possible PK/QTc modeling, appropriate ECG measures will be taken.

As this is healthy participant study, the use of concomitant medications in this study is expected to be minimal. Nevertheless, according to the DDI risk assessment for sisunatovir as described in [Section 2.2.2](#), sisunatovir is a moderate inhibitor of CYP3A4 and is projected to be a weak inhibitor of CYP2B6. For this reason sensitive and naïve to CYP3A4 substrates and sensitive naïve to CYP2B6 substrates are prohibited in this study. Since sisunatovir is a Pgp and CYP3A4 substrate, strong and moderate CYP3A4 inhibitors and strong Pgp inhibitors are also prohibited. Lastly, due to risk of MATE1 and OCT1 inhibition, sensitive substrates of these transporters are prohibited.

CCI

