6.1.1.3. Periods 4-7 (Cohort 1 only)

During Periods 4-7, participants will be assessing the taste of sisunatovir in a variety of vehicles using the questionnaire in [Appendix 10](#). Participants will taste 50 mg of sisunatovir in 7 ml of the following vehicles: water, saline, apple juice, and infant formula, given in a randomized order. Participants will swirl the study intervention in their mouth for 10 seconds and then spit it out. Participants will assess various aspects of the taste using the questionnaire in [Appendix 10](#): Oral Solution or Suspension Palatability Questionnaire at approximately 1 minute, 5 minutes, 10 minutes, and 20 minutes after spitting. There will be at least 60 minutes between tasting each study intervention, and at least 60 minutes after meals. Participants may eat plain crackers and water to cleanse their palate between assessments.

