6.4. Blinding

The first 2 periods of each cohort are double blind (sponsor open) design.

Study intervention administrated in Periods 3 to 7 of the study will be open to the participant, Investigator and Sponsor or Sponsor-designate personnel responsible for study monitoring activities (including all site monitoring activities).

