8.5.1. Palatability Questionnaire

Participants will be asked to fill out the Palatability Questionnaire after sisunatovir administration for treatments E, F, G, and H. The Palatability Questionnaire will be administered at 1 (immediately after sisunatovir administration), 5, 10, and 20 minutes after sisunatovir administration.

Details of the Palatability Questionnaire are provided in [Appendix 10](#).

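### SAP 3.5.1 credits late Cohort 1 adverse events to a spat-out vehicle and gives 400 mg fed and 400 mg fasted unequal event windows

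*SAP*

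**What the plan says.** SAP section 3.5.1 has two attribution rules. Events within 28-35 days "after the last dose of study intervention will be counted as treatment emergent and attributed to the last treatment taken". Events in a washout between periods are counted as "treatment emergent and attributed to the previous treatment taken". Neither rule mentions Periods 4-7.

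The protocol treats the Cohort 1 tastings as treatments:

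- Section 6.4: "Study intervention administrated in Periods 3 to 7 of the study will be open to the participant".
- Section 8.5.1 schedules the questionnaire "after sisunatovir administration for treatments E, F, G, and H".
- Section 6.1 lists the palatability product as an IMP.
- Section 1.3 marks study intervention administration for these periods and calls the gap between them a washout: "There is an at least 60 minute washout between tasting each dose in vehicle".

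The product is not swallowed. Section 6.1.1.3 says: "Participants will swirl the study intervention in their mouth for 10 seconds and then spit it out". On timing, section 1.3 says: "After the last PK draw for Period 3 participants will immediately start Period 4". Section 4.2 sets at least 48 hours between the last Period 3 dose and the tastings, partly to allow "complete assessment of and AEs associated with the multiple dosing scheme".

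Section 4.3 says Period 3 is there to compare PK, safety and tolerability fasted with fed in the same participants. Protocol section 9.3.1 and SAP section 5.2 call for reporting by treatment and, where applicable, by fed or fasted condition. SAP section 6.6.1 leaves the adverse event layout to sponsor standards that are not reproduced, and SAP section 2.1 lists no modifications to the protocol analysis.

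**The concern.** For any Cohort 1 participant who completes the tastings, the last treatment taken is a vehicle held in the mouth for seconds. A mechanical reading of the rule therefore puts the entire follow-up under water, infant formula, apple juice or saline, and puts events between tastings under the preceding vehicle. An event four days after the last 400 mg dose counts under A if that dose was fed, but under a vehicle if it was fasted.

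TEAEs are part of the primary endpoint. With no true difference between fed and fasted dosing, the shorter window alone would make fasted dosing look better tolerated. In optional Cohort 2, which has no tastings, the same rule gives the fasted regimen the full follow-up. The imbalance then runs the other way, and pooling the cohorts would mix the two.

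**Working it through.** The documents give no figure for these windows, so they are built from the stated timings. The sample size is empirical, so there is no power calculation to reproduce.

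**Inputs**

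- Dosing span in Periods 1-3: Day 1 morning dose to Day 5 morning dose (protocol 6.1.1), 96 h = 4 days.
- Last dose of A, B or C to the next treatment: at least 7 days (protocol 4.1), 168 h.
- Last dose of D to the first tasting: 48 h. Protocol 4.2 sets this as a minimum; section 1.3 places the tastings on Day 7 of Period 3, directly after the last PK draw.
- Follow-up: 28 to 35 days after the final dose (protocol 1.3).
- Half-life: 7-10 h (protocol 2.2.4).
- Cohort 1 size: 4 sequences × 3 = 12.

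**Windows under the rule as written** (dosing span plus time to the next study intervention)

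| Treatment | Calculation | Days from first dose |
|---|---|---|
| A, B, C | 4 + 7 | at least 11 |
| D, Cohort 1 | 4 + 2 | about 6 |
| Fasted regimen, Cohort 2 | 4 + 28 to 4 + 35 | 32 to 39 |

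- A to D ratio in Cohort 1, whole window: 11/6 = 1.83 or more.
- A to D ratio after last dose only: 7/2 = 3.5 or more.
- Follow-up credited to the last vehicle: 12 × 28 = 336 to 12 × 35 = 420 participant-days for 12 completers. D has 12 × 2 = 24 post-dose participant-days.

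**What 48 hours covers.** 48/10 = 4.8 and 48/7 = 6.9 half-lives, so about 0.5^4.8 = 3.6% to 0.5^6.9 = 0.9% of drug remains. Acute events on dosing, including most gastrointestinal events, fall inside D's window.

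**Illustration of size.** The documents give no background adverse event rate. Assume a constant rate r per participant-day and no true difference; the share with at least one TEAE in w days is 1 − exp(−r × w).

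| r (assumed) | A, 11 days | D, 6 days | Expected in 12 people, A vs D | Gap |
|---|---|---|---|---|
| 0.01 | 10.4% | 5.8% | 1.25 vs 0.70 | about 0.6 |
| 0.02 | 19.8% | 11.3% | 2.37 vs 1.36 | about 1.0 |
| 0.05 | 42.3% | 25.9% | 5.08 vs 3.11 | about 2.0 |

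**Does excepting the tastings cure it?** No. Returning all Cohort 1 follow-up to D gives 6 + 28 = 34 to 6 + 35 = 41 days, against at least 11 for A. The imbalance reverses, so a common cut-off is needed as well.

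**The case against.** The strongest reply is that little of consequence is touched:

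- A, B and C all fall in Periods 1-2, each followed by a washout of at least 7 days, so the randomized, blinded safety comparison uses one rule and one minimum window.
- The fed versus fasted tolerability question is mainly about gastrointestinal events, which 48 hours largely captures, and the listed food-effect objective is PK only.
- No hypothesis is tested, and A versus D is already confounded with period and open-label status.
- The rates in the illustration are chosen, and a constant rate weights outpatient washout days like in-house dosing days. If events cluster on dosing days, the gap shrinks.
- The sponsor standards might handle the display. Every event is recorded with an investigator causality assessment, so nothing is lost.
- A 48-hour window drops from the fed versus fasted table the very late events said to be misplaced.

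Most of this stands as a limit on reach. It does not remove the error. Protocol 4.3 makes safety and tolerability part of the Period 3 comparison. Causality is judged against study intervention and does not change the column in which an event is counted. The unseen standards cannot be assumed to override the study-specific rule in SAP 3.5.1, although the final table layout is for the same reason an inference. A 48-hour window does take late events out of the A versus D counts, but equally for both treatments, and they can still be shown separately.

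**Conclusion.** The concern holds and should be fixed. As written, the rule assigns 28-35 days of Cohort 1 follow-up to a spat-out vehicle and leaves D about 6 days from first dose against at least 11 for A. These windows follow directly from the stated timings, for participants who enter Period 4; someone who stops earlier has follow-up events attributed to the last Part 1 treatment.

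The effect is confined to the descriptive by-treatment TEAE tabulation: late-onset events, A versus D, the E to H columns, and any pooling with Cohort 2. Event collection, causality assessment and the A, B, C comparison are unaffected. The gap of 0.6 to 2.0 people in 12 is an illustration that depends on the assumed rates and their constancy, not an estimate of what will occur.

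**What to change.** Amend SAP sections 3.5.1 and 6.6.1 as follows.

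1. For fed versus fasted, tabulate TEAEs for A to D in one common window, from first dose to 48 hours after last dose, paired by participant for A versus D. This window is in-house in Periods 1-3 and ends before any tasting.
2. Do not attribute Cohort 1 events to a vehicle by default. Show events from the first tasting through follow-up in a separate post-Period 3 category, listed against D as the last swallowed regimen and kept outside the common-window counts. Place under E to H only events judged due to tasting.
3. Do not simply add the follow-up to D's main TEAE count, for the reason shown in the working.

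The cost is SAP wording, one programming rule and one extra adverse event table, all from data already collected. The drawback is that some tasting-related events may be listed against D. Because that category stays outside the common window, this cannot distort the A versus D counts.
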